During each condition, a movement disorder's specialist will conduct an assessment of items 3.1, 3.3(a-e), 3.9, 3.11, 3.12, 3.13 of MDS-UPDRS III. Afterwards, each participant will be outfitted with full body Opal sensors (APDM, Opal, and Portland, OR) affixed to the wrists, feet, sternum and lumbar spine (L5 level). A trained research coordinator will instruct each participant to conduct the Stand and Walk (SAW) test. During this test, subjects will stand for 30 seconds quietly, then walk 7 meters at their comfortable speed, turn 180 degrees, and walk back. Walking aides will be permissible, if needed. Unless the participant is unable to do so, the SAW test will be conducted twice for each trial in order to capture a sufficient number of gait cycles. Based on normative spatial-temporal gait analysis in healthy young and elderly adults (44-46), we selected the following measurements to be assessed during this instrumented walk: 1) Postural sway – root mean square (RMS) sway in antero-posterior (AP) and medio-lateral (ML) planes; 2) Gait – cycle duration (seconds), speed (m/s), stance (%), swing (%), heel strike angle (degrees), toe off angle (degrees), stride length (cm), cadence (steps/min), step duration (seconds), elevation at midswing (cm) (foot clearance), double support (%), arm swing velocity (deg/s), and range of motion (degrees); 3) Circumduction – turn angle (degrees), turn duration (seconds), and turn velocity (deg/s).

Following the gait testing, participants will undergo tremor and bradykinesia analysis with the Kinesia inertial sensors (Great Lakes Technologies, OH) that will be affixed to their finger and ankle. While seated, subjects will be guided through a series of movement tasks by interacting with the ONE tablet from Kinesia. Each motor test will appear on the touch screen interface that will instruct the participant on the motor task. The following tasks will be performed to assess bradykinesia: finger taps, hand grasps, wrist rotation, toe taps and leg lifts. The tremor assessments will be determined from the following tasks: arms resting (resting tremor), arms extended (postural tremor), and finger to nose (action tremor). Each motor task will last 15 seconds.

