Phase II. The primary goal of Phase II is to investigate the impact of stimulation frequencies (low and high), stimulation spatial characteristics and levodopa on gait kinematic domains. Participants will be evaluated in two conditions: 1) OFF medication/ON stimulation; 2) ON medication/ON stimulation. Patient's weight will be collected prior to this assessment. For chronic DBS patients, phase II will commence during study visit 1. For preoperative subjects, phase II will be conducted on a separate visit (study visit #2) that will take place 12-15 weeks after initial programming of bilateral STN deep brain stimulation implantation. This visit will also be conducted in a laboratory setting. The impact of the lesion effect from the surgery would also be avoided with this timeframe.

During condition (1), patients will be evaluated following overnight withdrawal of dopaminergic medications. Afterwards, each electrode contact will be reprogrammed by the Lead Principal Investigator in both low frequency and HFS. For each of the 4 contacts on both electrodes, the amplitude will be slowly increased by 0.1-V increment until sustained sensory or motor side effects are produced in HFS. The amplitude below the side effect threshold will be used along with a standard pulse width of 60 μ s. For low frequency stimulation (LFS) programming, milliamps will be adjusted to keep the

total electrical energy delivered (TEED) between both LFS and HFS conditions equivalent for each respective contact. The TEED is calculated as milliamp² x frequency x pulse width/impedance (47).

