The opal body sensors (APDM, Opal, Portland, OR) will be fixed to each subject's wrists, ankles, sternum and lumbar spine and the SAW task will be carried out by the research coordinator for each combination of low and high frequency stimulation for the four contact pairs (total of 8 trials with each contact pair being either LFS or HFS, exclusively; refer to Figure 1). The gait measurements will be the same as in Phase I. Bradykinesia and tremor assessments will be conducted for each combination of stimulation and contact pairs using the Kinesia inertial sensors (Great Lakes Technologies, OH) as well. Ratings of items 3.1, 3.3 (a-e), 3.9, 3.11, 3.12, 3.13 of MDS-UPDRS III will also be conducted for each stimulation-contact pairing. Following each stimulation parameter change, there will be a 10-minute latency before the gait task is conducted. The participants will be blinded to each stimulation change.

During condition (2), the stimulators will be turned off and subjects will be given 1.5 times their usual levodopa dose (up to 300mg) to ensure transition to the medication ON state. Retesting will be done 1 hour after the levodopa challenge (or sooner based on patient report and visual confirmation by physician). Gait, bradykinesia and tremor sensor assessments as well as MDS-UPDRS III rigidity and axial subscore ratings will be conducted in the same manner as condition (1). The participants will be blinded to stimulation changes. At the completion of Visit 2, participants will return to their initial programming settings and resume their medication regimen as per their standard of care. If participant fatigue develops, he/she will have the option to complete condition (2) on another visit within a 4 week time period.

Beginning September 2020, and until the COVID-19 pandemic has passed, all subjects who are not fully vaccinated against COVID-19 will be tested for COVID-19 prior to participation (as outlined in Section 10.2). As a result, remote consent will be employed during the COVID-19 pandemic (see Section 8.2). COVID-19 tests will be performed by nasopharyngeal swab at a Northwell facility, the cost of which will be billed to the study fund.

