Aim 2.1. We will utilize the raw data collected during Phase II to develop regression models, under both ON and OFF medication states for all contact pairs. The top panel in Figure 2 presents the overview of Aim 2.1; the goal of this sub-Aim is to predict the gait parameters for patients on low frequency by using the gait sensor measurements obtained on high frequency. Additional independent variables/regressors include general patient/disease characteristics such as age, gender, and disease duration. We will also build models under both ON and OFF medications. To develop the regression models, we use non-linear regression analysis based on random forest (RF) classifier. RF is based on an ensemble of decision trees, referred to as a 'forest,' where predictions for any new observation are obtained from averaging the predictions of individual trees (56). Generally, RF models are not prone to overfitting and are robust against noisy or high-dimensional datasets (57). In addition, they are generally interpretable, allowing for further examination of results and easier subject subtyping with respect to symptomology. However, to assure that the RF based models are the best performing models, we also develop models based on some of the other machine learning techniques, such as neural networks (56), and use them as benchmarks. If needed, to improve model performance we will perform model building in RF models to identify and include the most important parameters (38). We will use techniques such as cross-validation (e.g., leave-one-out) and bootstrapping to examine the generalizability of the models and acquire confidence intervals for the predicted values. Lastly, we will compare the best performing models obtained for both ON and OFF medications and their most important contributing parameters to further investigate the interaction of medications and stimulation frequency.

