Aim 2.2. Similar to Aim 2.1, in this sub-Aim we conduct regression analysis to predict gait parameters. However, in this sub-Aim, gait parameters are predicted on low and high frequency in the context of ON and OFF medication conditions using baseline bradykinesia, tremor, and gait sensor measurements, plus MDS-UPDRS III rigidity and axial sub scores. Patient and disease characteristics will be used as regressors. Again, models will be based on RF classifier, where other modeling techniques, such as neural networks, will be used as benchmarks. The best performing parameters identified in Aim 2.1 will be used to guide the model building in this sub-Aim. Also, aforementioned performance enhancing techniques will be used, if possible, and confidence intervals will be generated using bootstrapping. These models will be able to predict the best stimulation frequency and contact pairs for the patient immediately after baseline evaluations and provide a confidence level. Similar to Aim 2.1, we will

develop these models with and without accounting for PD medications to further quantify their impact and provide additional options for patients.

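### Section 9.4.2 does not make the patient the unit of cross-validation and bootstrapping for Aim 2; if pooled records are left out singly, accuracy for a new patient is overstated

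*Combined protocol and SAP*

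**What the plan says.** **Data per patient (section 4.1).** Phase II has two conditions, "1) OFF medication/ON stimulation; 2) ON medication/ON stimulation". Each condition has a "total of 8 trials with each contact pair being either LFS or HFS, exclusively". Unless the participant cannot manage it, "the SAW test will be conducted twice for each trial in order to capture a sufficient number of gait cycles".

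**Aim 2.1 (section 9.4.2).** The plan states: "We will utilize the raw data collected during Phase II to develop regression models", in both medication states and for all contact pairs. Gait on 60 Hz (LFS) is predicted from gait on high frequency (HFS). "Additional independent variables/regressors include general patient/disease characteristics such as age, gender, and disease duration". The validation sentence is: "We will use techniques such as cross-validation (e.g., leave-one-out) and bootstrapping to examine the generalizability of the models".

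**Aim 2.2 (section 9.4.2).** Gait at both frequencies is predicted "using baseline bradykinesia, tremor, and gait sensor measurements, plus MDS-UPDRS III rigidity and axial sub scores". On validation it adds: "aforementioned performance enhancing techniques will be used, if possible, and confidence intervals will be generated using bootstrapping".

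The text of these sections does not say whether the unit left out or resampled is a patient, a trial or a walk. Nor does it say whether contact pairs and medication states share one model or are modelled separately.

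**The concern.** Both aims are about a patient the model has not seen. Section 9.4.2 says the Aim 2.2 models will recommend a frequency and contact pair straight after the baseline evaluation. Only a split that keeps whole patients apart measures that.

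If rows are pooled and dropped one at a time, the forest trains on other walks by the patient it is tested on. In Aim 2.2 the baseline predictors are the same for every stimulation setting of a patient within a medication state, so they act as a patient label. In Aim 2.1 age together with disease duration does nearly the same. Part of the apparent accuracy is then the likeness between one person's walks.

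Aim 1 handles the repeated measures with a mixed model. Aim 2 uses the same repeated records and states no equivalent protection. Section 9.4.2 notes that forests are not prone to overfitting, but that does not help when the test patient's own data are in the training set. According to section 2.1 the results are meant to prepare a randomized trial of selecting patients for 60 Hz.

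**Working it through.** **1. Plan's own figure.** The plan gives no accuracy target or sample size for Aim 2. The only design figure is the 24 patients of section 9.2, which reproduces: 15.79 × 0.03 / 0.14² = 24.17. The simulations use 24 patients.

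**2. Records per patient.** 4 contact pairs × 2 frequencies × 2 medication states = 16 conditions, or 32 walks if both walks stay as separate rows. A fully pooled Aim 2.1 model has 4 × 2 = 8 LFS target records per patient. A fully pooled Aim 2.2 model has 16.

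**3. Overlap between training and test data.** Leaving out one record keeps k − 1 records of the same patient in training: 7 for Aim 2.1 and 15 for Aim 2.2. In a bootstrap of R rows, the chance that at least one sibling of a given record is drawn is 1 − (1 − (k − 1)/R)^R:
- k = 4, R = 96: 0.95
- k = 8, R = 192: 0.999
- k = 16, R = 384: above 0.999

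**4. Interval width.** For a simple mean, a record-level bootstrap understates the standard error by √(1 + (k − 1) × ICC). ICC is the share of variance lying between patients.
- k = 8: √3.1 = 1.8 at ICC 0.3; √7.3 = 2.7 at ICC 0.9
- k = 16: √5.5 = 2.3 at ICC 0.3; √14.5 = 3.8 at ICC 0.9

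**5. Pooled Aim 2.2 model with nothing to predict.** Setting: 24 patients × 16 records; 18 noise baseline variables plus age, gender and disease duration, all constant within patient; indicators for contact pair, medication and frequency; a random forest of 40 trees; 10 data sets per row. Record-level validation used 24 folds. The ICC is assumed.

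| ICC | Mean R², records left out | Mean R², patients left out | Record-level correlation test significant |
|---|---|---|---|
| 0 | −0.27 | −0.06 | 1 of 10 |
| 0.3 | 0.09 | −0.14 | 10 of 10 |
| 0.5 | 0.38 | −0.20 | 10 of 10 |
| 0.7 | 0.54 | −0.24 | 10 of 10 |
| 0.9 | 0.88 | −0.30 | 10 of 10 |

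A separate simulation with 4 records per patient, 91 noise baseline variables and exact leave-one-record-out (2 to 3 runs) gave 0.21, 0.61 and 0.81 at ICC 0.5, 0.7 and 0.9. With patients left out it gave −0.06 to −0.14. A further check at ICC 0.5 gave 0.37 by record and −0.13 by patient.

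**6. Only two rows per patient.** With 24 patients, 20 noise predictors and 4 to 5 runs, record-level R² was 0.10, 0.29 and 0.62 at ICC 0.5, 0.7 and 0.9. Patient-level R² was −0.27, −0.32 and −0.41.

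**7. Aim 2.1 with true prediction.** Setting: 24 patients × 4 records; 18 HFS parameters; HFS and LFS patient effects correlated 0.9 for four parameters (assumed); 4 runs.

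| ICC | R² by record | R² by patient | Difference |
|---|---|---|---|
| 0.5 | 0.20 | 0.12 | 0.08 |
| 0.7 | 0.40 | 0.27 | 0.13 |
| 0.9 | 0.75 | 0.53 | 0.22 |

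A separate check at ICC 0.5 gave 0.28 by record and 0.14 by patient, a difference of 0.14.

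**8. One row per patient.** With a separate model for each contact pair and medication state, ordinary leave-one-out already leaves out the patient. With nothing to predict, mean R² was −0.14 at ICC 0.7, so there is no inflation.

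**The case against.** The strongest reply is that the plan never commits to a record-level split. The methods are an open list with one example, and leave-one-out can mean leaving out one patient. Section 9.4.2 speaks of models in the plural and later compares the best ON and OFF models, which fits separate models by medication state. The second walk is there to collect enough gait cycles, which suggests one summary per trial. Figure 2, cited for Aim 2.1, could not be consulted for this review and may settle the question.

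Much of this stands. A reader might infer that the plan puts the test patient in the training set. The documents do not say so; they leave the unit open.

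A reader might also infer that Aim 2.1 would show accuracy where none exists. A pure null does not describe Aim 2.1, because what makes a patient's walks alike should also link HFS gait to LFS gait. The differences in step 7 are the fairer guide.

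Nor do the documents support saying that both Aim 2 endpoints could be declared statistically significant with no predictive value. Section 9.1 attaches statistical significance only to predicting 60 Hz gait from HFS gait, and it gives no metric or test.

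What does not stand is that the benign reading is safe. Raw data for all contact pairs suggests several rows per patient. Ranking frequencies and contact pairs makes pooling across settings natural. Aim 2.2 models are also built without accounting for medication, which may pool the two states. Step 6 shows that two rows per patient are enough to leak.

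**Conclusion.** The point holds conditionally. The validation unit is unstated, and the sentence applied literally to pooled records would overstate accuracy for a new patient and give intervals that are too narrow.

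For a pooled Aim 2.2 model with no true prediction, record-level R² is about nil or lower at ICC 0, at most about 0.1 at 0.3, about 0.2 to 0.4 at 0.5 and about 0.8 to 0.9 at 0.9. It is below zero on average with patients held out. For Aim 2.1 the overstatement is about 0.1 to 0.2 in R². If every model has exactly one row per patient, there is no effect.

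These sizes rest on assumed ICCs, 24 patients, simulated predictors and few runs per setting (2 to 10), so they show the order of magnitude only. The standard-error factors are for a simple mean and show direction rather than the exact width of prediction intervals. This is more than a missing detail, because an unstated choice could decide how a primary endpoint is reported.

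**What to change.** In section 9.4.2, replace the validation sentence with the following, and apply it to Aims 2.1 and 2.2 and to all benchmark models:

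*Generalizability is assessed by leave-one-patient-out cross-validation, with all settings, medication states and walks of a patient held out together; bootstrap samples are drawn by patient; any variable selection, tuning and model choice is done inside each training fold.*

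The last clause also covers the step in which the best parameters from Aim 2.1 guide Aim 2.2 on the same patients.

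The cost is one sentence and a grouping option in the code. Reported accuracy will be lower and intervals wider, because the effective sample becomes the 24 to 30 patients. If a patient-level split was always intended, stating it changes nothing else.

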9.2 SAMPLE SIZE DETERMINATION

To determine the sample size, we averaged the gait parameters (across all age groups) along with pooled variance captured on the APDM inertial sensors for healthy subjects (53) and PD patients with gait disorder (54) and computed a reasonable sample size of 24 (which equates to a Cohen's $d=0.8$) with a power of 0.80 and level of significance of 0.05. Assuming a 20% attrition rate, we will attempt to recruit 30 patients.

Sample Size estimation

$(\alpha) = 0.05, Z_\alpha = 1.96$
 $(\beta) = 0.80$

$$n = \frac{2(Z_a + Z_{1-\beta})^2 \sigma^2}{\Delta^2}$$

Reference Gait values for healthy individuals using APDM sensors

Age Groups	n	mean	STD	Variance
		normalized speed		
20-29	41	1.14	0.12	0.0144
30-39	41	1.16	0.14	0.0196
40-49	42	1.14	0.16	0.0256
50-59	45	1.21	0.14	0.0196
60-69	51	1.13	0.12	0.0144
70-89	72	0.86	0.23	0.0529

Ages 50-89: Mean Velocity - 1.06

Calculated Pooled Variance for Ages 50-89- 0.03

Calculated Pooled Variance for All ages – 0.03

Gait Parameters for PD patients with gait disorder (FOG- & FOG +) using APDM sensors

Walking Measure		Single Task Mean \pm STD
Stride Length (m)	FoG-	1.06 \pm 0.15
	FoG+	0.92 \pm 0.22
Stride Velocity (m/s)	FoG-	0.99 \pm 0.18
	FoG+	0.86 \pm 0.21

Average age 68 STD 8.4 (FOG -)

Average Age 69 STD 7.9 (FOG+)

Mean Velocity – 0.925 (FOG- & FOG+)

de Souza Fortaleza AC, Mancini M, Carlson-Kuhta P, King LA, Nutt JG, Chagas EF, Freitas IFJ, Horak FB. Dual task interference on postural sway, postural transitions and gait in people with Parkinson's disease and freezing of gait. *Gait Posture*. 2017;56:76-81.

Effect Size 1.06-0.925 = .14

$N = 15.79 (.03)/ (.14)^2 = 24 + 20\% \text{ attrition} = \text{total study recruitment } 29 \text{ subjects.}$

Final Study N= 30 subjects

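### Aim 2.1 studies the medication-by-frequency interaction by comparing ON and OFF models and their top parameters; at 24 to 30 patients these lists usually differ without any interaction, and no stated analysis estimates it

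*Combined protocol and SAP*

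**What the plan says.** Section 9.4.2, Aim 2.1, predicts gait on low-frequency stimulation (LFS) from gait measured on high-frequency stimulation (HFS), plus patient characteristics such as age, gender and disease duration. It does so in both medication states and over all contact pairs. Random forest is the lead method, with neural networks and similar techniques as benchmarks. The paragraph closes: "we will compare the best performing models obtained for both ON and OFF medications and their most important contributing parameters to further investigate the interaction" (medication by stimulation frequency).

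Cross-validation and bootstrapping are planned for generalizability and for intervals around predicted values. The text gives no list length, no measure of agreement, no interval for importances or for the ON-minus-OFF difference, and no rule for concluding that the two states differ.

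In each medication state a patient contributes a "total of 8 trials with each contact pair being either LFS or HFS, exclusively" (section 4.1).

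Section 9.1 hypothesises that levodopa and 60 Hz act synergistically on certain gait domains in some patients. For this, section 9.4.2, Aim 1.2, brings the levodopa-ON data into the mixed model and adds one binary levodopa variable. A product of levodopa and frequency is not mentioned.

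**The concern.** A medication-by-frequency interaction means that the LFS-minus-HFS difference in gait changes with levodopa. Comparing an ON model with an OFF model, each predicting LFS from HFS, does not estimate that quantity. Four features make the comparison hard to read:

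- Importance rankings are unstable at this sample size.
- Some predictors carry nearly the same information (stance and swing; cadence, step duration and cycle duration), and a forest can divide importance among them arbitrarily.
- The same patients supply both states, and the comparison is not planned as paired.
- The best model in one state may be a forest and in the other a neural network, whose importances are not on a common scale.

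The interplay of 60 Hz stimulation and medication is one of the questions in section 2.1 and a hypothesis in section 9.1. The Aim 2.1 sentence is the only place in section 9.4 that names the interaction. If chance differences between lists were read as interplay, nothing stated elsewhere would correct that reading.

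**Working it through.** **1. The plan's sample size.** Section 9.2 "computed a reasonable sample size of 24" "with a power of 0.80 and level of significance of 0.05", using "Effect Size 1.06-0.925 = .14" and "Calculated Pooled Variance for Ages 50-89- 0.03".

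- n = 15.79 × 0.03 / 0.14² = 0.4737 / 0.0196 = 24.17.
- With 2(1.96 + 0.8416)² as the constant, n = 24.03.
- Attrition: 24 × 1.2 = 28.8, so 29; or 24 / 0.8 = 30.

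The figure of 24 reproduces. It rests on healthy-versus-PD gait velocity, not on an interaction or on Aim 2.

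**2. Data available to each model.** Eight trials per state are 4 contact pairs × 2 frequencies, hence 4 LFS-HFS rows per patient. That is 24 × 4 = 96 to 30 × 4 = 120 rows per state. Section 9.4.2 states 20 gait measures, though its list counts to 2 sway + 13 gait + 3 turn = 18. Adding age, gender and disease duration gives 21 to 23 predictors.

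**3. Simulation with no interaction.** The same LFS-on-HFS relation held in ON and OFF, with 4 rows per patient, 20 gait and 3 patient predictors, and a forest fitted separately in each state. There were 150 runs per row. Assumptions not in the documents: list length 5, the R² and correlation values shown, half of predictor variance shared within patient, and the truth patterns.

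| Patients | True predictors | Correlation | R² | Top-five sets differ | Mean overlap of 5 | At least 2 differ | Top parameter differs |
|---|---|---|---|---|---|---|---|
| 24 | five equal | 0 | 0.5 | 95% | 3.19 | 63% | 63% |
| 24 | five equal | 0.5 | 0.5 | 99% | 2.45 | 89% | 78% |
| 24 | five equal | 0.5 | 0.7 | 95% | 2.86 | 75% | 73% |
| 24 | one dominant | 0.5 | 0.5 | 100% | 2.53 | 87% | 37% |
| 24 | one dominant | 0.5 | 0.7 | 99% | 2.78 | 81% | 17% |
| 24 | graded | 0.5 | 0.5 | 100% | 2.22 | 88% | 80% |
| 24 | diffuse | 0.5 | 0.5 | 100% | 1.95 | 96% | 88% |
| 30 | five equal | 0.5 | 0.5 | 100% | 2.55 | 85% | 74% |
| 30 | one dominant | 0.5 | 0.5 | 100% | 2.56 | 93% | 31% |
| 24 | five equal | 0 | 0.8 | 74% | 4.05 | 19% | 61% |

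Two lists of 5 drawn at random from 23 would share 5 × 5 / 23 = 1.09 on average. The lists therefore carry information, but agreement is far from complete.

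**4. Other simulation settings.** A further simulation with four rows per patient at 24 to 30 patients gave overlap of about 3 of 5 and identical lists in 2 to 5% of runs. The top parameter agreed in about 43 to 48% of runs with equal predictors and 98 to 100% with one dominant.

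Another set had 18 predictors in blocks correlated 0.6, R² 0.6, 24 patients, and residuals independent between rows. With four rows, overlap was 3.1 for equal predictors and 3.0 for one dominant. With a single true predictor it was 4.2, with identical lists in 40% of runs.

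**5. Sample size or method?** At 300 patients (25 runs each) the sets differed in 0% and 8% of runs with five equal predictors, but in 80% with one dominant. Instability is largely, not only, a matter of sample size.

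**6. A real interaction.** Adding 1 SD to LFS gait in the ON state only is a pure synergy. It gave 99% differing and overlap 2.45, the same as its no-interaction counterpart (row 2). The reason is simple: adding a constant to the outcome leaves every split of a regression tree unchanged.

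**The case against.** Aim 2.1 is about prediction, and its closing sentence is worded as supporting work. No test, threshold or claim is attached, and levodopa has its own sub-aim in the mixed model. All of that stands, and it rules out several stronger readings that a reader might infer:

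- *That the plan will report a spurious interaction, or has a false-positive rate of 74 to 100%.* With no decision rule there is no such rate. The percentages say only how often lists differ under the null.
- *That the comparison is made by eye.* The method of comparison is simply not given.
- *That no Aim 2.1 model contains medication.* Aim 2.2 describes models with and without accounting for medication and likens this to Aim 2.1, so the point is unsettled. The quoted sentence nevertheless compares ON with OFF models.
- *That even the top parameter is mostly noise.* The HFS value of the same parameter is a natural dominant predictor of its LFS value. With one dominant predictor the top rank agreed in 63 to 83% of runs in the table, and in 97 to 100% in the other settings. Treating the data as one row per patient gives a bleaker picture (overlap 1.9, top agreement 17%), but it ignores the four contact pairs.

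Two further limits apply. Correlations of 0.5 to 0.6 do not represent near-duplicates, so that mechanism is argued here, not measured. The authors may also intend a product term in Aim 1.2, although the text does not state one.

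None of this supplies uncertainty for the ON/OFF comparison or an estimate of the interaction.

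**Conclusion.** The concern holds in limited form. A difference between ON and OFF top-parameter lists is the usual result when no interaction exists. Across the tabulated scenarios the lists were not identical in about 74 to 100% of runs. Mean overlap was about 2 to 3 of 5, and about 4 in the most favourable scenario. The extreme case of a single true predictor still left 60% of runs differing. Equally, matching lists would not exclude a constant synergy in the ON state.

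The exact rates depend on the assumed list length, R², correlations and truth pattern. The direction held in every 24- and 30-patient scenario.

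The larger gap is in Aim 1.2: as written it gives a levodopa main effect, so no stated analysis estimates the synergy in section 9.1. It would be too strong to say that the study cannot address it. Each patient is tested in 2 × 8 = 16 combinations of medication, contact pair and frequency, so the term is estimable from the planned data. Section 9.2 does not address its power.

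**What to change.** **Section 9.4.2, Aim 1.2.** State that the mixed model contains levodopa, frequency and their product, with contact pair as in Aim 1.1. Report the product term with its interval for each outcome, apply the planned Holm adjustment across outcomes (after reconciling the stated 20 with the 18 listed), and draw interaction conclusions only from this term. Merely including medication and frequency as factors would not suffice. The term estimates an average over patients, whereas section 9.1 speaks of some patients; the text should acknowledge this.

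**Section 9.4.2, Aim 2.1.** Label the ON/OFF model comparison descriptive. Use the same algorithm in both states. Resample patients, keeping each patient's ON and OFF rows together, and report intervals for the ON-minus-OFF difference in prediction error and in grouped importance, with one group per set of redundant parameters. Keep all copies of a resampled patient in the same fold, or measure error on out-of-bag patients; otherwise the same patient sits in training and test data and error is understated. Do not use exclusion of zero as a claim rule, since many outcomes and groups would be examined without multiplicity control.

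**Cost.** SAP wording, computing time and fewer apparent findings. No new data, visits or change in procedures.
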